2.2 Secondary Objective(s)

To analyze the generic innate immune signatures that correlate with the persistence and the quality of the adaptive immune responses determined by serological assays to PPV23 and PCV13.

2.3 Exploratory Objective(s)

To compare the generic innate immune signatures that correlate with the magnitude of the adaptive immune responses (opsonophagocytosis [OPA] titers) in elderly and the young in the different age strata.

To compare the generic innate immune signatures that correlate with the persistence and the quality of the adaptive immune responses as determined by memory B cells, plasmablasts and monoclonal antibodies to PPV23 and PCV13.

3. STUDY DESIGN

This is a single center, mechanistic study in which 88 healthy subjects will be stratified by age with 22 subjects (ages 25-40) and 66 subjects (ages 60-89). and randomized to receive PPV23 or PCV13 in a 1:1 ratio.

Study volunteers will be recruited from the general population of metropolitan Atlanta. The study will be conducted at the Hope Clinic of the Emory Vaccine Center (Decatur, GA). The expected duration of subject participation is 6 months. An additional optional blood draw will be offered 2-3.5 years after enrollment.

3.1 Study Endpoints

3.1.1 Primary Endpoint(s)

- 3.1.1.1 Identification of generic innate immune signatures [Traditional immune parameters measurements + array-based gene expression] at days 1, 3 and 7 post vaccination with either PPV23 or PCV13 in the elderly.
- 3.1.1.2. Measurement of adaptive immune responses [Opsonophagocytosis assay (OPA) titers] at day 30 post vaccination with either PPV23 or PCV13 in the elderly.
- 3.1.1.3. Correlation of signatures of generic innate immune responses at days 1, 3 and 7 with adaptive immune responses [Opsonophagocytosis assay OPA titers] at day 30 post vaccination with either PPV23 or PCV13 in the elderly.

3.1.2 Secondary Endpoint(s)

- 3.1.2.1. Comparison of serotype specific IgG levels at day 30 post vaccination with either PPV23 or PCV13 in the elderly.
- 3.1.2.2. Correlation of signatures of generic innate immune responses at days 1, 3 and 7 that correlate to serotype specific IgG levels at day 30 post vaccination with either PPV23 or PCV13 in the elderly.
- 3.1.2.3. Comparison of the serotype specific avidity indexes in a subset of up to 6 vaccinees per vaccine group at day180 post vaccination with either PPV23 or PCV13 in the elderly.

- 3.1.2.4. Correlation signatures of generic innate immune responses at days 1, 3 and 7 that correlate to serotype specific avidity indexes in a subset of up to 6 vaccinees per vaccine group at day 180 post vaccination with either PPV23 or PCV13 in the elderly.
- 3.1.2.5. Comparison of the adaptive immune responses [Opsonophagocytosis assay (OPA) titers] at day 30 post vaccination with either PPV23 or PCV13 in the elderly.

3.1.3 Exploratory Endpoint(s)

3.1.3.1. Identification of correlation signatures of generic innate immune responses at days 1, 3 and 7 that correlate to adaptive immune responses [Opsonophagocytosis assay OPA titers specifically] at day 30 post vaccination among subjects in different age strata.

3.1.3.2. Comparison of the kinetics and magnitude of select serotype specific plasmablasts (days 7, 14, 30(with day 30 on a subset of vaccinees only)) and memory B cells (days 30, 180) post vaccination with either PPV23 or PCV13.

3.1.3.3. Comparison of the repertoire and monoclonal antibodies from plasmablasts in a subset of vaccinees per vaccine group at day 7 post vaccination with either PPV23 or PCV13.

3.1.3.4. Comparison of identified innate signature variables and correlation signature variables between PPV23 and PCV13 recipients.

3.1.3.5. Comparison of generic innate immune responses at days 1, 3 and 7 with adaptive immune responses [Opsonophagocytosis assay OPA titers and ELISA] at years 2-3.5 post vaccination with either PPV23 or PCV13.

Note: This will include - but not only - a comparison of identified innate signature variables and correlation signature variables between elderly (60 to 89 yo) recipients of PCV13 and young (25-40yo) recipients of PPV23.

3.2 Study Completion

This study will be considered "completed" when the primary and secondary objectives have been met. This includes the analysis of all the data required to meet the study objectives described above.

After the study is completed, the Principal Investigator (or co-PI) or Data Center will compile an abbreviated study reports. The study report will be reviewed by the ISM and submitted to the

local IRB and DAIT/NIAID. Alternatively, the publication of the study could be used for the purposes of this requirement.

4. SELECTION OF STUDY PARTICIPANTS

4.1 Inclusion Criteria

- 1. Able to understand and give informed consent.
- 2. Immunocompetent community dwelling subjects between the ages of 25-40 and 60-89 years.

4.2 Exclusion Criteria

- 1. Prior vaccination with pneumococcal vaccine.
- 2. Receipt of immune products
 - a. Subjects received blood products within 3 months*.
 - b. Subjects received of any live virus vaccines within 4 weeks prior to study entry or expected receipt within 4 weeks after study entry*.
 - c. Subjects received of any inactivated vaccine within 2 weeks or expected receipt within 2 weeks after study entry*.
- 3. Presence of co morbidities or immunosuppressive states such as:
 - Chronic medical problems including (but not limited to) insulin dependent diabetes, severe heart disease, severe lung disease, severe liver disease, cerebrospinal fluid leaks, severe kidney disease, autoimmune diseases, severe gastrointestinal diseases and grade 4 hypertension per CTCAE criteria**.
 - Alcohol, drug abuse or psychiatric conditions that in the opinion of the investigator would preclude compliance with the trial or interpretation of safety or endpoint data.
 - Impaired immune function or known chronic infections including, but not limited, to known HIV, hepatitis B or C; organ transplant; immunosuppression due to cancer; current and/or expected receipt of chemotherapy, radiation therapy, steroids*** (i.e., more than 20 mg of prednisone given daily or on alternative days for 2 weeks or more in the past 90 days, or high dose inhaled corticosteroids**** or any other immunosuppressive therapies (including anti-

TNF therapy), functional or anatomic asplenia and congenital immunodeficiency.

- 4. Conditions that could affect the safety of the volunteers such as:
 - Severe reactions to prior vaccinations.
 - An allergy to **any** component of the study vaccines (phenol, aluminum, CRM197 protein, succinic acid, Polysorbate 80).
 - History of Guillain-Barré syndrome.
 - History of bleeding disorders.

5. Volunteers with any acute illness* including, but not limited to, fever (> 100.4 F [> 38 C], regardless of the route) within 3 days prior to study entry.

6. Volunteers with social conditions or occupational conditions or any condition that in the opinion of the investigator might interfere with compliance with the study and vaccine evaluation.

7. Pregnant or breast feeding or women expected to conceive within 30 days after vaccination *****

*An individual who initially is excluded from study participation based on one or more of the time-limited exclusion criteria (e.g., acute illness, receipt or expected receipt of live or inactivated vaccines) may be reconsidered for enrollment once the condition has resolved as long as the subject continues to meet all other entry criteria.

** Grade 4 hypertension per CTCAE criteria is defined as Life-threatening consequences (e.g., malignant hypertension, transient or permanent neurologic deficit, hypertensive crisis) urgent intervention indicated.

***Subjects receiving > 20 mg/day of prednisone or its equivalent daily or on alternate days for more than 2 weeks may enter the study after therapy has been discontinued for more than 3 months.

****High dose ICS is defined as: > 960 mcg/day of beclomethasone dipropionate or equivalent.

***** Women of child-bearing potential (not surgically sterile via tubal ligation, bilateral oophorectomy or hysterectomy or who are not postmenopausal for ≥ 1 year) must agree to practice adequate contraception that may include, but is not limited to, abstinence, monogamous relationship with vasectomized partner, barrier methods such as condoms,

diaphragms, spermicides, intrauterine devices, and licensed hormonal methods for 30 days before and 30 days after receiving PPV23 or PCV13.

4.3 Early Study Termination

Participants may be terminated early from the study for the following reasons:

a. The participant elects to withdraw consent from all future study activities, including followup.

b. The participant is considered by the PI to be "lost to follow-up" (i.e., no further follow-up is possible because attempts to reestablish contact with the participant have failed).

c. The participant dies.

d. The participant develops a medical condition or is started on new medication(s) not previously mentioned in the list of prohibited medications that, in the opinion of the investigator, may pose additional risks from participation in the study, may interfere with the participant's ability to comply with study requirements or that may impact the quality of the data obtained from the study.

e. Blood not able to be drawn (for technical or other reasons) or participant not tolerating multiple blood draw attempts.

f. As deemed necessary by the PI or her designee for noncompliance or other reasons.

g. As deemed necessary by the PI after development related AE/SAE.

h. The participant meets the individual stopping rule -delineated in section 8.

Participants with early termination from this study may be replaced as needed to preserve the statistical power needed to prove the primary endpoint (Refer to section 9.1).

Note:

Up to the discretion of the PI, participants receiving prohibited medications before blood draw at day 30 (+/-7 days) or missing any of the blood draws required for the primary endpoint [meaning draws at days 1, 3, 7(\pm 1), and 30 (\pm 7)] may still continue with the scheduled study blood draws required for secondary and exploratory study endpoints.

Subjects receiving prohibited medications before blood draw at day 30 (+/-7 days) or missing any of the blood draws required for the primary endpoint [meaning draws at days 1, 3, 7(\pm 1), and 30 (\pm 7)], along with participants with early termination from this study for any reason may

be replaced as needed to preserve the statistical power needed to prove the primary endpoint. (Refer to section 9.1) HIPC: VAX-003

5. INVESTIGATIONAL PRODUCT(S)/INTERVENTION MATERIAL(S), OTHER STUDY PRODUCTS (CONTROLS/PLACEBOS)

5.1 Investigational Product(s)/Intervention(s)

The Emory Investigational Drug Service will purchase PNEUMOVAX® 23 from its manufacturer (Merck, Whitehouse Station, NJ) and PREVNAR®13 from its manufacturer (Pfizer, New York, NY) or their distributors. The Emory Investigational Drug Service will store the vaccines and will monitor temperatures of refrigerator containing the vaccines.

Refer to section 1.6, and applicable product labeling for known and potential risks to human participants associated with the investigational product(s) intervention(s).

5.2 Formulation, Packaging, and Labeling

PNEUMOVAX® 23 (Pneumococcal Vaccine Polyvalent) is a sterile, liquid vaccine for intramuscular or subcutaneous injection. It consists of a mixture of highly purified capsular polysaccharides from the 23 most prevalent or invasive pneumococcal types of *Streptococcus pneumoniae*, including the serotypes that most frequently cause invasive drug-resistant pneumococcal infections among children and adults in the United States.

| 23 Pneumococcal Capsular Types Included in PNEUMOVAX 23 | | |
|--|---|--|
| Nomenclature | Pneumococcal Types | |
| | | |
| Danish | 1 2 3 4 5 6B** 7F 8 9N 9V** 10A 11A 12F 14** 15B 17F 18C 19F** 19A** 20 22F 23F** 33F | |
| ** These serotypes most frequently cause drug-resistant pneumococcal infections ¹ | | |

PNEUMOVAX 23 is manufactured according to methods developed by the Merck Research Laboratories. Each 0.5 mL dose of vaccine contains 25 micrograms of each polysaccharide type in isotonic saline solution containing 0.25% phenol as a preservative.

PNEUMOVAX 23 will be supplied as a single-dose vial of liquid vaccine.

PREVNAR 13®, Pneumococcal 13-valent Conjugate Vaccine (Diphtheria CRM197 Protein) is a sterile suspension of saccharides of the capsular antigens of *Streptococcus pneumonia* serotypes 1, 3, 4, 5, 6A, 6B, 7F, 9V, 14, 18C, 19A, 19F, and 23F, individually linked to nontoxic diphtheria CRM197 protein. Each serotype is grown in soy peptone broth. The individual polysaccharides

are purified through centrifugation, precipitation, ultrafiltration, and column chromatography. The polysaccharides are chemically activated to make saccharides, which are directly conjugated by reductive amination to the protein carrier CRM197, to form the glycoconjugate. The individual glycoconjugates are compounded to formulate Prevnar®13. Potency of the formulated vaccine is determined by quantification of each of the saccharide antigens and by the saccharide to protein ratios in the individual glycoconjugates. Each 0.5 mL dose of the vaccine is formulated to contain approximately 2.2 µg of each of *Streptococcus pneumoniae* serotypes 1, 3, 4, 5, 6A, 7F, 9V, 14, 18C, 19A, 19F, 23F saccharides, 4.4 µg of 6B saccharides, 34 µg CRM197 carrier protein, 100 µg polysorbate 80, 295 µg succinate buffer and 125 µg aluminum as aluminum phosphate adjuvant.

Note: No additional labeling of the vaccines will be required

5.3 **Preparation, Administration, and Dosage**

PNEUMOVAX®23:

Vaccine vials will be stored at +2°C to +8°C (36°F to 46°F) and administered per label as below:

The vaccine will first be inspected visually for particulate matter and discoloration prior to administration and will not be used if particulate matter or discoloration is found. The vaccine is used directly as supplied. No dilution or reconstitution is necessary.

A single 0.5 mL dose of PNEUMOVAX®23 will be administered via the intramuscular route in the deltoid muscle.

PREVNAR®13:

Vaccine vials will be stored at +2°C to +8°C (36°F to 46°F) and administered per label as below: The vaccine will first be inspected visually for particulate matter and discoloration prior to administration and will not be used if particulate matter or discoloration is found. The prefilled syringe will be shaken vigorously immediately prior to use to obtain a homogenous, white suspension in the vaccine container.

A single 0.5 mL dose of PREVNAR®13 will be administered via the intramuscular route in the deltoid muscle.
5.4 Accountability of Investigational Product(s)/Intervention(s)

Under Title 21 of the Code of Federal Regulations (21CFR §312.62) the investigator will maintain adequate records of the disposition of the investigational product(s)/intervention material(s), including the, date and quantity of the drug received, to whom the drug was dispensed (participant-by-participant accounting), and a detailed accounting of any investigational product(s)/intervention material(s) accidentally or deliberately destroyed.

Records for receipt, storage, use, and disposition will be maintained by the study site. A dispensing log will be kept current for each participant. This log will contain the identification of each participant, the name of the vaccine administered to the subject, the lot of vaccine received by the subject and the date and quantity of vaccine dispensed.

All records regarding the disposition of the investigational product(s)/intervention material(s) will be available for inspection by the site monitor, the health authorities, and DAIT/NIAID personnel.

5.5 Assessment of Compliance with Investigational Product(s)/Intervention Material(s)

Number of used vaccine vials will be tracked and reconciled by the nursing staff prior to sending the vaccine back to the Emory Investigational Drug Service.

5.6 Modification or Discontinuation of Investigational Product(s)/Intervention Material(s)

5.6.1 Modification of Investigational Product(s)/Intervention(s)

Unless the lots of PNEUMOVAX®23 or PREVNAR®13 used in the study are recalled by the manufacturers, there will be no discontinuation of administration of study vaccines.

5.6.2 Premature Discontinuation of Investigational Product(s)/Intervention(s)

Refer to sections 4.3 for possible causes of early study termination.

If a subject withdraws from the study for any reason, the subject will be then be censored from the study.

Refer to section 8.1.3 for safety follow-up after early study termination.

6. **OTHER MEDICATIONS**

6.1 Concomitant Medications

In accordance with exclusion criteria, subjects expected to receive prohibited medications (see section 6.4) will be considered non-eligible for the study. All medications, therapies or vaccines administered to study subjects after study entry will be documented at each visit.

6.2 **Prophylactic Medications**

Prophylactic medications will not be administered before vaccination or any study procedure.

6.3 **Rescue Medications**

We do not anticipate the use of any rescue medication; however should anaphylactic or hypersensitivity reactions occur, an epinephrine (1:1000) and diphenhydramine injections are readily available at the Hope Clinic during vaccine use.

When facing a medical emergency, the clinic staff will follow the institutional Hope Clinic SOP by calling 911 first. If needed, participant will be transferred to Emory University Emergency department for further care.

Subjects are allowed to use acetaminophen or NSAIDs if they experience a moderate to severe local or systemic side effects after vaccine administration.

6.4 Concomitant Study Medications

All medications and vaccines received by study participants after administration of study vaccine should be reported to the study staff and recorded including (but not limited to) the following:

- blood products, chemotherapy, immunosuppressive therapy (including anti-INF therapy) and radiation therapy (administered at any time after study vaccination)

- inactivated vaccines (administered before the day 14 blood draw)

- live-attenuated vaccine (administered before the day 30 blood draw)

Any of the above medications can affect the innate and adaptive assay results and should not be used unless medically indicated.

Up to the discretion of the PI, participants receiving concomitant medications may still continue with scheduled study blood draws. Subjects receiving concomitant medications, along with participants with early termination from this study for any reason, may be replaced as needed to preserve the statistical power needed to prove the primary endpoint. (Refer to section 9.1.).

HIPC: VAX-003

7. STUDY VISITS AND PROCEDURES

7.1 Enrollment and Randomization

This research study will be explained in lay terms to each potential research participant. The potential participant will sign an informed consent form before undergoing any study procedures. Participants who are deemed eligible for the study (see sections 4.1 and 4.2) will be enrolled and assigned a unique participant number. Approximately eighteen months are needed for enrollment. The duration of participation for each subject is approximately 6 months. An additional optional blood draw will be offered 2-3.5 years after enrollment.

Eighty eight subjects (22 subjects (ages 25-40) and 66 subjects (ages 60-89)) will be randomized to receive PPV23 or PCV13 in a 1:1 ratio.

7.2 Screening Visit(s)

Refer to 7.3

7.3 Baseline Visit(s)

Interested subjects will call recruiters for a telephone screening where the eligibility criteria of the subject will be reviewed. To confirm that participant has never received pneumococcal vaccine in the past, vaccination records may be requested from participant's physician after obtaining a release of information from the participant. If the subject is found to be eligible and continues to be interested in participating after reading the informed consent (emailed or mailed to him/her), an appointment will be scheduled.

Study staff will review with the subject the study informed consent form and will answer all questions related to the study. Once the subject signs the informed consent, a study participation number will be assigned and subject will be randomized to receive PPV23 or PCV13. The participant will be asked to provide demographic information and information related to his/her medical history including current medications and vaccination history to verify eligibility. The volunteer's vital signs will be recorded and a targeted physical exam will only be performed if needed based on findings during review of health status. For female volunteers of age bearing potential, a urine pregnancy test is obtained. Only females with a

CONFIDENTIAL

negative urine pregnancy test will be enrolled in the study. Females of child bearing potential will be asked to use effective contraceptive method thirty days before and 30 days after vaccination. Blood for immunological assays will be drawn at this visit. For female participants aged 25-40 blood for immunological assays will be drawn after results of the urine pregnancy test are available and shown to be negative.

The participant will get the pneumococcal Vaccine Information Sheet and then receive 1 dose per label of either PNEUMOVAX®23 or PREVNAR®13 according results of randomization.

Any Adverse Event (including – but not only- vaccine reactions and local or systemic Reactogenicity Events) of grade 3 or higher severity or any SAE occurring after vaccination while the subjects is still at the clinical site will be recorded and reported.

The participant will be provided with a written description of what represents a local and systemic vaccine reaction of mild, moderate and severe intensity (Refer to Appendix 3 and Appendix 4). Subjects will be instructed to notify the study center by telephone if they develop any severe reactions within 1 week following vaccination.

At the end of the visit, the participant will also be instructed to promptly call the site if he/she develops any of the following:

- becomes sick or has been treated at the doctor's office or emergency department or has been hospitalized for any illness throughout D180 of the study;
- develops any adverse event that limits self-care activities of daily living (e.g. bathing, dressing and undressing, feeding self, using the toilet, taking medications, and not bed ridden) even if he/she decides not to get medical care; or
- starts or stops any medications/therapies during enrollment in the study.
- Becomes pregnant.

Refer to section 8.2.5 for safety data that must be recorded and reported.

Note: Subjects calling the site for any of the above will receive further instructions on the proper course of action, including a return to the clinic for immediate evaluation if appropriate. The Baseline visit will last approximately 90 minutes.

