7.8 Study Arm Assignment Procedures

7.8.1 Blinding and Randomization

In this study 88 healthy subjects 22 subjects (ages 25-40) and 66 subjects (ages 60-89)) will be randomized to receive PPV23 or PCV13 in a 1:1 ratio.

The randomization of the pre-filled vaccine syringes will be performed by the Emory Investigational Drug Service.

7.8.2 Securing Randomization Information

The information on and randomization is kept at the Emory Investigational Drug Service.

7.8.3 Requirements for Unblinding

HIPC: VAX-003 is an open study. Subjects will be made aware of which vaccine they are receiving at the time of vaccine administration and will be informed about:1. the need for a second dose of vaccine depending on age at entry and randomization status.2. the commitment of the investigators to inform subjects if any changes in recommendations for revaccination develop during subject's participation in the study.

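### Section 7.3 numbers and randomises at consent, before on-site eligibility checks and the pregnancy test, which conflicts with section 7.1 and allows exclusions after allocation in an open study

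*Combined protocol and SAP*

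**What the plan says.** Section 7.3 (Baseline Visit) starts with a remote step: "Interested subjects will call recruiters for a telephone screening where the eligibility criteria of the subject will be reviewed". To confirm that a volunteer has had no earlier pneumococcal vaccine, "vaccination records may be requested from participant's physician". Only those who pass are given an appointment.

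At the appointment, after the consent discussion, the rule is: "Once the subject signs the informed consent, a study participation number will be assigned and subject will be randomized to receive PPV23 or PCV13". The next sentence has the participant supply demographic details and "medical history including current medications and vaccination history to verify eligibility". Vital signs, a physical examination if needed, and the pregnancy test follow. Of women of child-bearing potential, only those with a "negative urine pregnancy test will be enrolled in the study".

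Section 7.1 (Enrollment and Randomization) gives a different order: "Participants who are deemed eligible for the study (see sections 4.1 and 4.2) will be enrolled and assigned a unique participant number".

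Section 7.8 says "HIPC: VAX-003 is an open study". It has the investigational drug service randomise the syringes and keep the randomisation information, and it tells subjects their vaccine when it is administered. Section 9.1 leaves the details of the randomisation process to the manual of procedures.

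**The concern.** Eligibility is normally settled before allocation, so that nothing about the assigned arm can influence who stays in. Section 7.3 reverses this for the on-site checks. Some of those checks involve judgement: exclusions 3 and 6 in section 4.2 rest partly on the investigator's opinion about compliance and interference with evaluation. Others can change after the telephone call, such as acute illness or fever in the three days before entry.

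If an allocation already exists when these decisions are made, and the person deciding knows it, exclusions could differ by arm. Even if nobody knows it, a subject who fails has been randomised and is then lost. What is at stake is whether the two vaccine groups, as analysed, are still the groups that randomisation created.

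**Working it through.** **1. The plan's own figures.** Section 9.1 recruits 88 and assumes 10% attrition: 88 × 0.90 = 79.2, stated as 80. In the elderly, 66 / 2 = 33 per arm and 33 × 0.90 = 29.7, stated as 30. At n = 30 the stated power of 80% reproduces: 79.7% for effect size 0.66 (alpha 0.01), 79.8% for 0.88 (alpha 0.0005), 79.2% for correlation 0.57 (alpha 0.01) and 79.0% for correlation 0.60 (alpha 0.005). None of these figures depends on the order of steps at Day 0, so the point turns on comparing the texts.

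**2. The order of steps.**

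| Source | Order |
|---|---|
| 7.1 | judged eligible → enrolled and numbered (timing of randomisation not stated) |
| 7.3 | telephone screen → consent → numbered and randomised → history to verify eligibility, vital signs, pregnancy test → vaccine |

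**3. Where the conflict lies.** The direct clash is over enrolment and numbering: section 7.1 makes both follow eligibility, while section 7.3 numbers at consent. Section 7.1 does not itself time randomisation. But section 7.3 ties numbering and randomisation to the same moment, so if numbering must wait for eligibility, randomisation has to wait with it. Section 7.3 is also at odds with itself: the pregnancy test decides enrolment, yet the women tested have by then been numbered and randomised.

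**4. Appendix 1 does not settle it.** The schedule lists eligibility above number assignment and randomisation. It also lists the pregnancy test and blood draw below vaccination, although section 7.3 makes a negative test a condition of enrolment and section 1.1 places the baseline sample before the vaccine. Its row order is therefore not reliable evidence of sequence.

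**5. What happens to a subject who fails on site.** The subject is numbered and randomised but not vaccinated. Sections 9.2.1 and 9.2.2 define the analysis population differently in the blood draws they require, but both demand vaccination per label. The subject therefore leaves every endpoint analysis. Sections 4.3, 8.1.4 and 9.1 allow replacement or extra recruitment.

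**6. Which analyses are exposed.**
- Primary endpoints 1 and 3 are analysed within each elderly arm, and endpoint 2 is descriptive by arm. None is a test between vaccines.
- Secondary endpoints 1 (IgG), 3 (avidity) and 5 (OPA) are unpaired tests of PPV23 against PCV13, and several exploratory endpoints compare the vaccines. These rely on comparable arms.
- The pregnancy test concerns, in practice, the 25-40 group (11 per arm), which section 9.2.1 confines to exploratory endpoints.

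**7. Size.** The documents give no rate of exclusion between randomisation and vaccination. The 5 to 10% in section 9.1 is attrition during the study from all causes. Purely as an assumption, if 5% or 10% of an elderly arm were lost at this step and nothing else were lost, 33 × 0.95 = 31.35 or 33 × 0.90 = 29.7 would remain.

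**The case against.** The strongest reply is that this is a matter of wording with a hypothetical consequence. The criteria have already been reviewed by telephone, so the visit confirms an earlier decision and few should fail. The order of sentences need not be the order of conduct. The drug service holds the randomisation, subjects hear their vaccine only at administration, and the manual of procedures may already delay disclosure. The study is exploratory, its primary analyses are within arm, and the replacement rules protect the numbers.

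Much of this stands. It limits the likely number of late failures and confines the risk to the between-vaccine comparisons. It does not remove the conflict. The rule in section 7.3 opens with an explicit time marker, so it is more than narrative order. Telephone review is weaker than verification in person, and requesting vaccination records is optional. Drug-service custody does not tell us whether site staff know the arm while they complete the checks, because the documents do not say. Replacement adds subjects but does not bring back those removed after allocation.

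A reader might go further and infer that staff will select by arm because the study is open. The documents do not support that: open-label status does not establish that the allocation is known during verification.

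**Conclusion.** The point holds as a conflict between sections 7.3 and 7.1 that should be corrected. As written, section 7.3 permits exclusions after randomisation, and those subjects vanish from every endpoint analysis. Selection by arm is possible, not demonstrated. The consequence would fall chiefly on secondary endpoints 1, 3 and 5 and the exploratory vaccine comparisons.

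A reader might also infer that the order of steps costs power by taking an elderly arm below 30. That is not supported. No rate is given. On the assumed losses above, the expected arm size falls below 30 only at 10%, and then to the same 29.7 that the plan already accepts after attrition. Adding such losses to planned attrition would give lower numbers, but only by ignoring replacement and the section 9.1 commitment to recruit further if more than 10% of the 88 miss a required draw.

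The conclusion assumes that section 7.3 is followed literally. If the manual of procedures already holds back allocation until the checks are complete, the practical risk largely disappears and only the protocol text needs correcting.

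**What to change.** Reword section 7.3 to agree with section 7.1: consent; completion of the on-site eligibility checks (medical, medication and vaccination history, acute illness, investigator-opinion exclusions and, where applicable, a negative pregnancy test); then number assignment and randomisation, with the drug service releasing the allocation only at that point. Make the manual of procedures match. Drawing the Day 0 blood before randomisation is optional.

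Add a line to section 9.2.4 requiring a count by arm, with reasons, of anyone randomised but not vaccinated. That section currently covers study status and reasons for leaving but does not ask for them by arm.

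The reordering also avoids a question the protocol leaves open: whether a subject deferred for a time-limited exclusion, whom section 4.2 allows to be reconsidered, keeps an allocation already made.

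The cost is a few sentences of text and one reporting line. All the steps already take place at the single Day 0 visit, so no visit, test or sample is added. The only operational change is that release of the vaccine waits for the eligibility checks to finish.
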